## 2.7 **EBV Viremia, Disease Activity and EBV-specific T cells**

It is standard of care to monitor serial EBV PCRs in EBV-naïve patients for at least the first two years post solid organ transplant to detect EBV viremia (as an indication of either primary seroconversion or EBV reactivation) early and be able to intervene with reduction of immunosuppression to prevent PTLD. Reduction in immunosuppression leads to autologous EBV specific immune reconstitution. EBV viremia inversely correlates with the presence of EBV-specific T cells and can predict risk for relapse as shown in previous publications using autologous EBV-specific T cells. In addition, Wilsdorf et al. showed in 11 pediatric SOT recipients who had been treated for PTLD that a strong autologous EBV-specific T-cell expansion in response to EBV viremia is capable of preventing relapse and of controlling EBV viremia. A secondary aim on this study is to further characterize the correlation of EBV viremia, EBV-specific T cells and risk of relapse.

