#### 9.7 Correlative Studies

We will summarize the *in vivo* measurements of virus-specific T cells over the pre-LMP-specific T cells to the post-LMP-specific T cells monitoring period in patients who receive LMP-specific T cells versus patients who do not to assess the pattern and magnitude of T-cell expansion and persistence for EBV and response to LMP-specific T cells administration using plots generated for each patient to graphically illustrate the pattern and duration of LMP-specific T-cell persistence and expansion. The area under the curve (AUC) will be calculated for each subject by the trapezoidal rule. The AUCs will be summarized, and after logarithmic transformation, will be analyzed by a two-sample *t*-test. Measurements of immunity, tetramer analysis and functional assays will be evaluated by descriptive statistics (means, standard deviations, medians and ranges) at each time point and analyzed by paired *t*-tests to compare changes from pre- to post-infusion.

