# Time point calculated from Day 0 of LMP-TC1 regardless of treatment on Course LMP-TC2.

### 15.2 Blood Sample Collection

15.2.1 Whenever a specimen collection time falls on a treatment infusion day, blood must be drawn prior to initiation of the infusion.

15.2.2 The indicated time points in the table above represent the ideal schedule. Flexibility is expected in order to coordinate with times of blood draw for regular clinical care:

- After Course LMP-TC1 or RTX2 or during follow-up time points at Week 6, Week 8 and Months 2 & 3: variations of up to 2 days before/after scheduled dates are acceptable.
- For the later time points Months 6, 9, 12: variations of up to 4 weeks are acceptable.

15.2.3 Missed Time Points: If biology specimens are not obtained at any requested time point, please send specimens at the next requested time point or at the next clinic visit, whichever is sooner. Please note that EBV PCR is a required specimen on this study.

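### Section 9.7 compares T-cell expansion between non-randomised groups on an AUC with no baseline term, so any difference in pre-infusion level enters the test in full

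*Combined protocol and SAP*

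**What the plan says.** Section 9.7 (Correlative Studies) summarises virus-specific T cells "in patients who receive LMP-specific T cells versus patients who do not to assess the pattern and magnitude of T-cell expansion and persistence". The measurements run "over the pre-LMP-specific T cells to the post-LMP-specific T cells monitoring period", so the pre-infusion level lies inside the curve.

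The summary measure is defined in one sentence: "The area under the curve (AUC) will be calculated for each subject by the trapezoidal rule". The AUCs, "after logarithmic transformation, will be analyzed by a two-sample *t*-test". No subtraction of baseline, ratio to baseline, incremental AUC or covariate is given. Appendix IV.4 only refers back to Section 9.7.

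The one analysis in Section 9.7 that uses the pre-infusion value is within patients. Immunity measurements, tetramer and functional assays are to be "analyzed by paired *t*-tests to compare changes from pre- to post-infusion".

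A pre-infusion sample exists in both arms. Section 15.1 schedules draws on Day 0 of LMP-TC1 and Day 1 of RTX2, and Section 15.2.1 says: "Whenever a specimen collection time falls on a treatment infusion day, blood must be drawn prior to initiation of the infusion".

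**The concern.** Expansion is a change from a starting value. Appendix IV treats it that way in its ELISPOT paragraph, which takes a rise of at least 0.5 log between successive time points as significant expansion. A raw AUC is instead the starting level carried forward over time plus whatever change occurs. A t-test on its logarithm has equal total level as its null hypothesis, not equal expansion.

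This matters because the groups cannot be presumed alike at the start. Under Section 4.1.2, Arm RTX is Cohort A in complete response after Induction. Arm LMP-TC is the rest of Cohort A plus all relapsed and refractory patients. The optional biology samples start at RTX2 or LMP-TC1, so Arm RTX is in practice the comparison group.

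At stake is the reading of Appendix IV's hypothesis that LMP-specific T cells with rituximab reconstitute immunity better than rituximab alone. A significant log-AUC difference could be reported as expansion when it is only a difference in starting level, and a null result could conceal a real effect.

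**Working it through.** The documents give no SD, power, alpha or sample size for this test, so there is no stated figure to reproduce.

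**1. Algebra (no assumed numbers).** Write a patient's level as baseline B times a relative profile f(t). Then

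log AUC = log B + log ∫f(t)dt.

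The two-sample contrast is the difference in mean log B plus the difference in mean log ∫f. Only the second term is expansion. The first enters with coefficient 1.

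**2. Inputs for size.**
- From the documents: target of 30 patients on Arm LMP-TC (Section 9.1); sampling on LMP-TC1 Days 0, 7, 14, 28, 41 and Week 8, and on RTX2 Days 1, 8, 15, 21 and Weeks 6 and 8 (Section 15.1).
- Assumed: 25 patients in Arm RTX; between-patient SD 0.5 or 0.7 log10; within-patient SD 0.25 log10; two-sided 5% test; expansion half present by Day 7 and full from Day 14.

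**3. Closed-form check, no expansion, SD 0.5, ignoring within-patient noise.** SE = 0.5 × √(1/30 + 1/25) = 0.5 × 0.2708 = 0.1354. The critical t on 53 df is 2.006.
- Baseline difference 0.25: 0.25/0.1354 = 1.846; P(Z > 2.006 − 1.846) ≈ 44%.
- Baseline difference 0.35: 0.35/0.1354 = 2.585; P(Z > 2.006 − 2.585) ≈ 72%.

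**4. Simulation (30 v 25).** Planned test: t-test on log10 AUC. Corrected test: t-test on log10(AUC/window length) − log10(own pre-infusion value). Ranges show agreement between repeat runs.

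| Expansion in LMP-TC (log10) | LMP-TC baseline | Planned, SD 0.5 | Planned, SD 0.7 | Corrected |
|---|---|---|---|---|
| 0 | 0.25 lower | 43–44% | 24–26% | 5–6% |
| 0 | 0.35 lower | 68–70% | 42% | 5–6% |
| 0.5 | 0.35 lower | 9–11% | 9–10% | 100% |
| 0.3 | equal | 47% | 27% | 95–97% |
| 0.5 | equal | 89% | 64% | – |

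The false-rejection rates are the same if the imbalance runs the other way.

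**5. Other assumed inputs.** Take within-patient SD 0.2, between-patient SD 0.3 to 0.8, and groups of 30/30, 20/15 or 30/45. With no expansion, the planned test rejects in 19% to 98% of trials at a 0.3 log10 baseline difference and in 44% to 100% at 0.5. The corrected test rejects in 3.9% to 5.7%. Adjusting log AUC for log baseline as a covariate helps less, because a single noisy baseline adjusts incompletely: at SD 0.5 and 30/30 it rejects in 11.8% and 21.8% for differences of 0.3 and 0.5.

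**6. When does correction cost power?** Let σb and σw be the between- and within-patient SDs, and w0 the trapezoid weight of the Day 0 sample. Over 56 days w0 = 3.5/56 = 0.0625. Treating noise on the log scale as approximately additive:
- Var(raw) = σb² + σw²Σw²
- Var(corrected) = σw²(1 + Σw² − 2w0)

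Correction reduces variance when σb² > σw²(1 − 2 × 0.0625) = 0.875σw², that is σb > 0.935σw. Simulation agrees (equal baselines, 0.3 log10 expansion, 30 v 25). At σb = σw = 0.5 the two tests are about level (planned 42%, corrected 46%). At σb = 0.3 and σw = 0.4 the corrected test is worse (62–64% against 78%).

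**The case against.** The strongest reply has four parts.

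*Within-patient change is already tested.* The paired t-tests in Section 9.7 cover tetramer and functional assays, which are the protocol's virus-specific T-cell measures, and patient plots are added. This stands, but those tests make no comparison between groups.

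*Total level is a proper target.* The stated purpose is "to assess the pattern and magnitude of T-cell expansion and persistence for EBV", which includes persistence, and immune reconstitution concerns the level reached and held. This stands. A reader might infer that the raw AUC is invalid and should be replaced; the documents do not support that. It answers a different question from expansion.

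*The power loss depends on chosen inputs.* A reader might infer that most power is lost even when baselines are equal. That does not hold generally. At Appendix IV's own 0.5 log step, with equal baselines and SD 0.5, the planned test has 89% power, and where within-patient noise is large the correction loses power.

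*Direction is unknown.* Section 2.7 reports that "a strong autologous EBV-specific T-cell expansion in response to EBV viremia is capable of preventing relapse", and one might infer that relapsed and refractory patients start lower, so that the plan would mask a true effect. That sentence rests on 11 treated patients and concerns expansion in response to viremia. It does not give pre-infusion levels by disease status.

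It is also fair to say that the false-rejection figures arise from non-comparable groups. Baseline correction removes the part due to starting level only. The corrected 5–6% assumes that both groups would follow the same time course without the T cells.

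**Conclusion.** The concern holds for the between-group test of expansion. That an imbalance in pre-infusion level passes fully into the log-AUC contrast follows from the algebra alone. The groups are not randomised, and nothing elsewhere in the documents repairs it. The size is illustrative: about 44% to 70% rejection with no expansion for a 0.25 to 0.35 log10 baseline difference, against about 5% after correction, at assumed SDs of 0.5 and 0.25 and 30 versus 25 patients. The documents supply neither these SDs nor any imbalance, and optional biology consent may make the groups smaller.

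The consequence is limited. These are exploratory, optional-consent analyses with no decision rule attached. The primary feasibility endpoint, the monitoring rules and treatment assignment are unaffected.

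**What to change.** In Section 9.7, separate the two questions.

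- **Expansion, between groups:** apply the two-sample t-test to log10(time-averaged AUC) minus log10 of the patient's own pre-infusion value (Day 0 of LMP-TC1 or Day 1 of RTX2), over a common window to Week 8. State the value to be used when the baseline is below the detection limit.
- **Total level and persistence:** keep the raw log-AUC comparison, and state that it is not to be read as expansion.

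The cost is a sentence or two and no new samples. Patients without a usable baseline sample drop out of the expansion test. Correction can lose power if within-patient noise is as large as the between-patient spread or larger. It does not remove other confounding between the non-randomised groups, and the text should say so.

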## 10.0 EVALUATION CRITERIA

### 10.1 Common Terminology Criteria for Adverse Events (CTCAE)

This study will utilize version 5.0 of the CTCAE of the National Cancer Institute (NCI) for toxicity and performance reporting. A copy of the CTCAE version 5.0 can be downloaded from the CTEP website

([http://ctep.cancer.gov/protocolDevelopment/electronic\\_applications/ctc.htm](http://ctep.cancer.gov/protocolDevelopment/electronic_applications/ctc.htm)).

Additionally, toxicities are to be reported on the appropriate case report forms.

Please note: 'CTCAE v5.0' is understood to represent the most current version of CTCAE v5.0 as referenced on the CTEP website (i.e., v5.02 and all subsequent iterations prior to version 6.0).

### 10.2 Response Criteria

Response and progression will be evaluated in this study using the new international criteria proposed by the revised Response Evaluation Criteria in Pediatric Non-Hodgkin Lymphoma Criteria, with modification from the Lugano classification for all patients with measurable disease. Patients with evaluable disease of the GI tract will have to be evaluated by endoscopy and biopsies.

#### 10.2.1 Induction: RTX for all non-refractory patients

For the purposes of this study, patients will be evaluated for response Week 3 of Induction (RTX1).

#### 10.2.2 Arm RTX

In addition to a baseline scan or endoscopy with biopsies, confirmatory scans and/or endoscopy with biopsies should also be obtained at the end of Course RTX2.

#### 10.2.3 Arm LMP-TC

In addition to a baseline scan and/or endoscopy with biopsies, additional scans and/or endoscopy with biopsies to document response need to be obtained at the end of Course LMP-TC1 during Week 6 of that course. For patients assigned to Course LMP-TC2, there will be an additional evaluation time point with scans scheduled at week 6 of LMP-TC2.

For patients found to have progressive disease (PD) at either one of those evaluations, it is recommended to repeat scans in a 2-4 week time frame as per the Lugano classification to confirm progressive disease prior to changing therapy because inflammatory responses to LMP-specific T cells have been reported with a corresponding initial increase in size and metabolic uptake of involved lymph nodes.

#### 10.2.4 Definitions

10.2.4.1 Evaluable for toxicity: A patient will be considered for toxicity monitoring if the patient is eligible and one of the following occurs: (1) completes one course of protocol therapy; (2) dies on protocol therapy for a reason considered possibly, probably, or likely related to protocol therapy; or (3) is removed from protocol therapy because of an adverse

experience possibly, probably, or likely related to one of the agents.

10.2.4.2 **Evaluable for objective response:** Only those patients who have measurable disease present at baseline and have received at least one dose of protocol therapy will be considered evaluable for response. These patients will have their response classified according to the definitions stated below. (Note: Patients who exhibit objective disease progression prior to the end of Course 1 will also be considered evaluable.)

#### 10.2.5 **Disease Parameters**

10.2.5.1 **Measurable disease:** A measurable node must have an LDi (longest diameter) greater than 1.5 cm. A measurable extranodal lesion should have an LDi greater than 1.0 cm. All tumor measurements must be recorded in millimeters (or decimal fractions of centimeters).

10.2.5.2 **Non-measured disease:** All other lesions (including nodal, extranodal, and assessable disease) should be followed as nonmeasured disease (e.g., cutaneous, GI, bone, spleen, liver, kidneys, pleural or pericardial effusions, ascites).

10.2.5.3 **Target lesions:** For patients staged with CT, up to six of the largest target nodes, nodal masses, or other lymphomatous lesions that are measurable in two diameters (longest diameter [LDi] and shortest diameter) should be identified from different body regions representative of the patient's overall disease burden and include mediastinal and retroperitoneal disease, if involved.

#### 10.2.6 **Methods for Evaluation of Measurable Disease**

All measurements should be taken and recorded in metric notation using a ruler or calipers. All baseline evaluations should be performed as closely as possible to the beginning of treatment and never more than 2 weeks prior to the beginning of the treatment.

The same method of assessment and the same technique should be used to characterize each identified and reported lesion at baseline and during follow-up. Imaging-based evaluation is preferred to evaluation by clinical examination unless the lesion(s) being followed cannot be imaged but are assessable by clinical exam.

10.2.6.1 **Clinical lesions:** Clinical lesions will only be considered measurable when they are superficial (e.g., skin nodules and palpable lymph nodes) and  $\geq 10$  mm diameter as assessed using calipers (e.g., skin nodules). In the case of skin lesions, documentation by color photography, including a ruler to estimate the size of the lesion, is recommended.

10.2.6.2 **Conventional CT and MRI:** The major response designations will be established by CT or MRI of involved sites in conjunction with morphologic evaluation of bone marrow (BM) if involved at diagnosis. With growing concerns about the risks of cumulative ionizing radiation exposure to children from CT, MRI could be considered as an alternative

to CT for evaluating non-pulmonary disease sites. e.g., assessment of abdominal/pelvic disease. As with CT, if an MRI is performed, the technical specifications of the scanning sequences used should be optimized for the evaluation of the type and site of disease. Furthermore, as with CT, the modality used at follow-up should be the same as was used at baseline and the lesions should be measured/assessed on the same pulse sequence. It is beyond the scope of the response guidelines to prescribe specific MRI pulse sequence parameters for all scanners, body parts, and diseases. Ideally, the same type of scanner should be used and the image acquisition protocol should be followed as closely as possible to prior scans. Pulse sequences should include at a minimum, axial and coronal fat-saturated FRFSE-T2, coronal T1 and axial and coronal post-gadolinium fat-saturated T1 weighted imaging. Body scans should be performed with breath-hold scanning techniques, if possible.

- 10.2.6.3 **PET-CT:** At present, the low dose or attenuation correction CT portion of a combined PET-CT is not always of optimal diagnostic CT quality. However, if the site can document that the CT performed as part of a PET-CT is of identical diagnostic quality to a diagnostic CT (with IV and oral contrast), then the CT portion of the PET-CT can be used for International Pediatric Non-Hodgkin Lymphoma Response Criteria measurements and can be used interchangeably with conventional CT in accurately measuring cancer lesions over time. Note, however, that the PET portion of the CT introduces additional data, which may bias an investigator if it is not routinely or serially performed.
- 10.2.6.4 **Ultrasound:** Ultrasound is not useful in assessment of lesion size and should not be used as a method of measurement. Ultrasound examinations cannot be reproduced in their entirety for independent review at a later date and, because they are operator dependent, it cannot be guaranteed that the same technique and measurements will be taken from one assessment to the next. If new lesions are identified by ultrasound in the course of the study, confirmation by CT or MRI is advised. If there is concern about radiation exposure at CT, MRI may be used instead of CT in selected instances.
- 10.2.6.5 **Endoscopy, Laparoscopy:** Endoscopy may be used in patients with evaluable disease of the GI tract to confirm complete pathological response by obtaining biopsies.
- 10.2.6.6 **Tumor markers:** There will be no use of tumor markers to assess response in the protocol. EBV qPCR of peripheral blood PBMCs will be performed centrally to measure the presence of active viral replication and disease activity but results will not be used to stratify assignment to treatment arms.
- 10.2.6.7 **FDG-PET:** For patients with a positive PET scan at diagnosis, PET can be used to follow response in addition to a CT scan using the International Pediatric Non-Hodgkin Lymphoma Response Criteria.

### 10.2.7 Response Criteria

#### 10.2.7.1 Evaluation of Measurable Disease

Complete Response (CR): *Disappearance of all disease.* CT or MRI should be free of residual mass or evidence of new disease. FDG-PET should be negative.

CR unconfirmed (Cru): Residual mass is negative by FDG-PET; no new lesions by imaging examination; no new and/or progressive disease elsewhere

Partial Response (PR): 50% decrease in SPD (the sum of the products of the largest diameter and the perpendicular diameter for a tumor mass) on CT or MRI; FDG-PET may be positive (Deauville score or 4 or 5 with reduced lesional uptake compared with baseline); no new and/or PD; morphologic evidence of disease may be present in BM if present at diagnosis; however, there should be 50% reduction in percentage of lymphoma cells

Progressive Disease (PD): For those with > 25% increase in SPD on CT or MRI, Deauville score 4 or 5 on FDG-PET with increase in lesional uptake from baseline, or development of new morphologic evidence of disease in BM

Stable Disease (SD): Neither sufficient shrinkage to qualify for PR nor sufficient increase to qualify for PD, taking as reference the smallest sum diameters while on study.

#### 10.2.7.2 Evaluation of Non-measured Lesions (CT-based response, PET/CT based response not applicable)

Complete Response (CR): Absent non-measured lesions.

Partial response (PR): Absent/normal, regressed, lesions, but no increase.

Stable Disease (SD): No increase consistent with progression

Progressive Disease (PD): New or clear progression of preexisting non-measured lesions.

#### 10.2.7.3 Evaluation of organ enlargement

Complete Response (CR):	Regress to normal
Partial response (PR):	Spleen must have regressed by > 50% in length beyond normal
Stable Disease (SD):	No increase consistent with progression
Progressive Disease (PD):	In the setting of splenomegaly, the splenic length must increase by 50% of the extent of its prior increase beyond baseline. If no prior splenomegaly, must increase by at least 2 cm from baseline.
	New or recurrent splenomegaly

#### 10.2.8 Duration of Response

10.2.8.1 Duration of overall response: The duration of overall response is measured from the time measurement criteria are met for CR or PR (whichever is first recorded) until the first date that recurrent or progressive disease is objectively documented (taking as reference for progressive disease the smallest measurements recorded since the treatment started).

The duration of overall CR is measured from the time measurement criteria are first met for CR until the first date that progressive disease is objectively documented.

10.2.8.2 Duration of stable disease: Stable disease is measured from the start of the treatment until the criteria for progression are met.

#### 10.2.9 Progression-Free Survival

PFS is defined as the duration of time from start of treatment to time of progression or death, whichever occurs first.

#### 10.2.10 Response Review

Response will be as per institutional evaluations.

## 11.0 ADVERSE EVENT REPORTING REQUIREMENTS

### 11.1 Purpose

Adverse event data collection and reporting, which are required as part of every clinical trial, are done to ensure the safety of patients enrolled in the studies as well as those who will enroll in future studies using similar agents. Certain adverse events must be reported in an expedited manner to allow for timelier monitoring of patient safety and care. The following sections provide information about expedited reporting.

### 11.2 Determination of Reporting Requirements

Reporting requirements may include the following considerations: 1) whether the patient has received an investigational or commercial agent; 2) the characteristics of the adverse event including the *grade* (severity), the *relationship to the study therapy* (attribution), and the *prior experience* (expectedness) of the adverse event; 3) the Phase (1, 2, or 3) of the trial; and 4) whether or not hospitalization or prolongation of hospitalization was associated with the event.

An investigational agent is a protocol drug administered under an Investigational New Drug Application (IND). In some instances, the investigational agent may be available commercially, but is actually being tested for indications not included in the approved package label.

Commercial agents are those agents not provided under an IND but obtained instead from a commercial source. The NCI, rather than a commercial distributor, may on some occasions distribute commercial agents for a trial.

When a study includes both investigational and commercial agents, the following rules apply.

- *Concurrent administration:* When an investigational agent is used in combination with a commercial agent, the combination is considered to be investigational and expedited reporting of adverse events would follow the guidelines for investigational agents.
- *Sequential administration:* When a study includes an investigational agent and a commercial agent on the same study arm, but the commercial agent is given for a period of time prior to starting the investigational agent, expedited reporting of adverse events which occur prior to starting the investigational agent would follow the guidelines for commercial agents. Once therapy with the investigational agent is initiated, all expedited reporting of adverse events follow the investigational agent reporting guidelines.

